1.1 Study objectives

The study objectives include:

- documenting characteristics of patients under specialist (psychiatric) care who are prescribed Seroquel XR as treatment for MDD in each of the selected countries over a 9 month period, starting 3 months following the launch of the product for its approved indication.
- describing the differences between countries concerning treatment practices involving use of Seroquel XR through the use of a drug utilisation questionnaire of psychiatrist in 5 European countries.

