2.1 Overall study design

This is a multinational, multicenter, retrospective, observational study of antidepressant drug utilisation among an inception cohort of patients under specialists (psychiatrists) care who are prescribed Seroquel XR for treatment of major depressive episodes associated with MDD following launch of the indication in each country. The study will be conducted in 5 European countries: Germany, Italy, Romania, Spain, and Sweden to ensure geographic representation across European member states. The sponsor may include alternate EU country(ies) based upon limited use of Seroquel XR for MDD in the countries listed and whose selection will maintain geographic representation among EU countries.

The inception cohort is defined as patients initiating Seroquel XR (as add-on therapy or as monotherapy) during a 9 month period corresponding to 3 to 12 months following the launch of the product in each country for the MDD indication. In the period immediately after launch, physicians may not be aware of the approval of Seroquel XR for add-on treatment for MDD. Therefore, patients treated with Seroquel XR within the 3 months after launch will not be included in the inception cohort because they are not likely to be representative of patients

[figure not shown]
treated in subsequent periods. A drug utilisation questionnaire will be used to collect study data. Data collection will be initiated following a study-defined index date, approximately 12 months after product launch. All study sites within a country will be assigned the same index date and will not be contacted prior to the index date.* Initiation of site-specific activities for selection of patient records meeting study selection criteria will commence on or following the index date. Data on drug utilisation will be censored on the index date. This approach will ensure that study procedures do not influence prescribing practices.

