3.2 Patient Selection

Each investigator will identify patients who meet criteria as having received SEROQUEL XR for MDD at any time in the 3-12 month period following launch in each country, and contact the patients to obtain informed consent. A listing of subjects will be generated according to patients' last name (or other convenient identifier).

Up to 30 subjects will be selected per site. The selection of eligible patients will proceed as follows:

1. For sites with 30 or fewer eligible patients, all will be included, provided that informed consent is given where required.
2. For sites with more than 30 eligible patients, random selection to assure lack of bias in the selection of 30 patients will be accomplished using an algorithm provided by AstraZeneca. Informed consent will be obtained to provide up to a maximum of 30 selected patients.

The limit of 30 patients per site is proposed to support the objective of having adequate representation of patients within a given country.

Site specific activities related to the selection of patient records will start on or following the index date. This approach should ensure that selection of patients will not be influenced by prescribing practices prior to the index date and prescribing practices are not influenced by study procedures.

If the number of eligible patients refusing to take part in the study exceeds 20% of the total sample in a country, readily identifiable basic demographic information (age range and gender) from patients refusing to participate will be requested and collated. This will permit an evaluation of the distribution of non-participants across sites and countries.

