3.3.1 Inclusion Criteria for Patients

1. Provision of informed consent before initiation of any collection of questionnaire data.
2. Female and male aged 18 years and over.
3. Documented clinical diagnosis of Major Depressive Disorder, Single Episode, or Recurrent.
4. Initiation of Seroquel XR for treatment of MDD during the period defining the inception cohort, i.e. from 3 months after launch until the index date.

The prescription of the medicinal product is clearly separated from the decision to include the patients in the study.

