4.2 Questionnaire Administration

4.2.1 Timeline for questionnaire administration

The exact index date for each country will be selected to optimise preparations leading to completion of drug utilisation questionnaires at all sites within a country following Good Pharmacoepidemiology Practices (PDS 2008).

Contact with investigators and site preparatory activities are initiated following the index date, which will correspond to a date approximately 12 months following the launch of Seroquel XR for MDD in each country.

Preparatory activities for completion of the drug utilisation questionnaires at each site will rely on automated and manual review of data from patient medical records in order to identify patients meeting study inclusion criteria. This selection includes consideration of the inception cohort definition (i.e., initiation of treatment with Seroquel XR in the time interval 3 months after launch up to the index date).

Once site preparatory activities are concluded, including the obtaining of informed consent from the patient, data abstraction of patient medical records using the drug utilisation questionnaire will begin.

Information on the Physician questionnaire related to physician characteristics will be completed based upon the best available recollection by the investigator. Patient questionnaire data will be abstracted from the medical records of the patients maintained at the official location for storage of records for the site/investigator and will be performed by a representative of AstraZeneca.

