
If you have specified a height for this patient, has it been:

- Measured?
- Estimated?
- Not specified?

What was the patient’s weight at the visit closest to *date 1 (date 1 = 9 months prior to [INDEX DATE])*

__ kg
 Not specified?

Date that weight was:

- measured?
- reported by patient ?
- not specified?

__ / __ / __
day / mo / year

What is the race of this patient?

- White
- Black
- Asian
- Other (including native people or mixed races) – please specify _____
- Not specified

Referral Pathways

When did the investigator see this patient for the first time?

__ / ____ (month / year)

mo / year

Who referred this patient to the investigator?

Please select one answer only

- Primary care physician
- Another psychiatrist (in-patient)
- Another psychiatrist (out-patient)
- Law enforcement
- Family member
- Accident & emergency
- Social services
- Self-referral
- Other – please specify _____

Why was this patient referred to the investigator?

Please select all that apply

- Specific need for psychiatric care
- Access to specific treatments
- Severity of MDD
- Concomitant disorders / complexity of psychiatric state
- Other – please specify _____

Medical/Psychiatric History

In the table below, please record if, according to the medical record, the patient has ever reported/experienced any of the following concomitant disorders? *Please select all that apply*
 Has the patient received **drug treatment** (in the past or current) for any of these conditions?

Please select all that apply

	Ever Experienced	If experienced, is the condition past /current Circle all that apply?	Received Drug treatment (in the past)	Receiving Drug treatment (currently)
Anxiety disorder(s)	Yes / No / Unknown	Past / Current	Yes / No / Unknown	Yes / No / Unknown
Alcohol abuse	Yes / No / Unknown	Past / Current	Yes / No / Unknown	Yes / No / Unknown
Nicotine use	Yes / No / Unknown	Past / Current	Yes / No / Unknown	Yes / No / Unknown
Illicit substance abuse	Yes / No / Unknown	Past / Current	Yes / No / Unknown	Yes / No / Unknown
Other Axis 1	Yes / No / Unknown Please specify 1) _____ 2) _____ 3) _____	Past / Current Past / Current Past / Current	Yes / No / Unknown Yes / No / Unknown Yes / No / Unknown	Yes / No / Unknown Yes / No / Unknown Yes / No / Unknown

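### The inception window ends at month 12 in some sections and at the index date in others, and the Patient Form's date 1 is counted back from the index date instead of forward from launch

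*Protocol*

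**What the plan says.** The Protocol describes the window in three ways.

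- **Fixed end.** Section 2.1 defines the inception cohort as patients starting the drug "during a 9 month period corresponding to 3 to 12 months following the launch of the product in each country for the MDD indication". Section 1.1 gives the same period: "over a 9 month period, starting 3 months following the launch of the product for its approved indication". Section 3.2 uses it too, but speaks of receipt and not of starting: "having received SEROQUEL XR for MDD at any time in the 3-12 month period following launch in each country".
- **End at the index date.** Inclusion criterion 4 (Section 3.3.1) requires initiation "from 3 months after launch until the index date". Section 4.2.1 gives this as the cohort definition: "initiation of treatment with Seroquel XR in the time interval 3 months after launch up to the index date".
- **Counted back from the index date.** The opening instruction of the Patient Form (Appendix B) covers patients prescribed the drug between date 1 and the index date. The weight item on that form defines the start: "date 1 = 9 months prior to [INDEX DATE".

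Sections 2.1 and 4.2.1 place the index date at about 12 months after launch, without a tolerance. Section 4.2.1 adds: "The exact index date for each country will be selected to optimise preparations leading to completion of drug utilisation questionnaires at all sites". Under Section 2.1 all sites in a country share one index date, and drug-utilisation data are censored on it. Section 3.3 allows no exceptions to the eligibility criteria.

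**The concern.** A patient who starts after month 12 but before a late index date satisfies an eligibility criterion that admits no exceptions, yet is not in the cohort that Section 2.1 defines. The Protocol does not say which statement governs.

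This matters because Section 2.1 itself treats time since launch as relevant to representativeness: that is its reason for leaving out the first three months. Describing differences between countries is an objective (Section 1.1), and Section 9 reports by country so that countries can be compared. If the end of the window moves with each country's logistics, part of an observed difference in prescribing may reflect time since launch.

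Date 1 adds a second problem, because its distance from launch moves with the index date. A third exists even when all the dates agree. Section 3.2 and the Patient Form speak of patients who *received* or were *prescribed* the drug during the period, whereas Section 2.1, criterion 4 and Section 4.2.1 require that treatment *started* in it.

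**Working it through.** Let T be the index date in months after launch.

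**Inputs.** Start of the window: month 3 (Sections 1.1, 2.1, 3.3.1, 4.2.1). Fixed end: month 12 (Section 2.1). End under criterion 4: T. Form interval: T − 9 to T (Appendix B). Censoring: T (Section 2.1).

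**The plan's own figure.** 12 − 3 = 9 months, as stated.

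**When the definitions agree.** Section 2.1 gives 3 to 12 and criterion 4 gives 3 to T, so they are equal only if T = 12. The form's start equals month 3 only if T − 9 = 3, which again gives T = 12.

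**Away from month 12.** No tolerance is given, so T = 10 to 14 is an assumed range. For T below 12 the Section 2.1 window is cut at T, because data are censored there.

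| T | Section 2.1 | Criterion 4 | Form interval | Discrepancy |
|---|---|---|---|---|
| 10 | 3–10 | 3–10 | 1–10 | date 1 is 2 months inside the excluded period; 2/9 = 22% of the form interval |
| 11 | 3–11 | 3–11 | 2–11 | date 1 is 1 month inside it; 1/9 = 11% |
| 12 | 3–12 | 3–12 | 3–12 | none |
| 13 | 3–12 | 3–13 | 4–13 | 1 month is in criterion 4 only; 1/10 = 10% of the criterion 4 window |
| 14 | 3–12 | 3–14 | 5–14 | 2 months are in criterion 4 only; 2/11 = 18% |

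For T above 12, the share of the criterion 4 window that lies outside Section 2.1 is (T − 12)/(T − 3). For T below 12, the share of the form interval that lies in the excluded period is (12 − T)/9. Both are shares of calendar time. They would be shares of starters only if initiation were uniform over time, and the Protocol gives no uptake figures.

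**What the form interval does.** It concerns prescribing, not starting. With T = 14, a patient who started in month 3 and was still prescribed the drug at month 5 is inside it. Only an eligible patient who stopped before month 5 falls outside.

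**Starting versus receiving, with T = 12.** A patient who started in month 2 and was still treated in month 5 fits the wording of Section 3.2 and of the Patient Form, but fails criterion 4.

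**The case against.** The strongest reply is that criterion 4 is the operative rule and the rest is loose wording. Section 4.2.1 has patients identified against the inclusion criteria and consented before abstraction with the form begins. Date 1 is defined inside a body-weight item, and its other use is a completion instruction for the person extracting the data. The analysis is descriptive, with no statistical comparison planned.

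Much of this stands, and it rules out three stronger conclusions that a reader might draw.

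- **That the form undoes the three-month exclusion.** Criterion 4 fixes the start at three months after launch and admits no exceptions, so a month-2 starter is ineligible wherever date 1 falls. The risk arises only if T is below 12 and the form's dates are used for selection.
- **That a late date 1 removes all early starters.** With T = 14, treating the form interval as an initiation window would leave only months 5 to 12 common to all three definitions, which is 7 of 11 months (64%). The form refers to prescribing, so that figure does not describe what it says.
- **That sites within a country will recruit over different windows because the index date is approximate.** They share one index date. Divergence arises between countries, or where sites follow different sections.

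For T below 12, Section 2.1 and criterion 4 also coincide in practice because of censoring.

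The reply does not remove the conflict between Section 2.1 and criterion 4 when T exceeds 12. That conflict lies in the body of the Protocol and does not depend on the form. A purely descriptive analysis still needs one definition of whom it describes.

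**Conclusion.** The concern holds in limited form. The cohort has two end points, which conflict whenever a country's index date falls after month 12. Date 1 on the Patient Form is wrongly anchored whenever the index date is not exactly month 12. The *received* and *prescribed* wording leaves room for misreading even at month 12.

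Under assumed index dates of month 13 and 14, the conflict covers 10% and 18% of the criterion 4 window in calendar time. With an early index date only the form departs, and criterion 4 still protects the three-month start. At exactly month 12 there is no date discrepancy. The actual effect on patients and on the country comparison depends on index dates and uptake that the Protocol does not give, so no bias of a particular size is shown. The inconsistency is cheap to remove and should be removed before sites select records.

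**What to change.** - State one initiation window, with the same start (launch plus 3 months) and the same end, in Sections 1.1, 2.1, 3.2, 3.3.1 and 4.2.1 and in the Patient Form instruction. One workable choice ends it at launch plus 12 months and requires that the index date be no earlier than that.
- In Appendix B, define date 1 as launch in that country plus 3 months.
- In Section 3.2 and the Patient Form instruction, replace the *received* and *prescribed* wording with *initiated*.
- Print the resulting calendar dates for each country on the form.
- Leave the trial-participation exclusion in Section 3.3.2 running to the index date. Drug-utilisation data are collected up to that date, so shortening the exclusion would admit patients who were in a trial while their utilisation was still being recorded.

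The cost is wording in the Protocol and form plus a table of dates per country. The reference date of the weight item moves with date 1. With a month-12 end, patients who start between month 12 and a late index date are not included. Changing date 1 alone would not be enough: it would align the form's start with criterion 4, but Section 2.1 would still end T − 12 months before criterion 4 in any country with a late index date.

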4.2.2 Key Variables - Psychiatrists, Subjects, and Drug Utilisation

The drug utilisation questionnaire is constructed to collect key variables on characteristics of physicians, patients and the drugs utilised in the medical management of depressive episodes in MDD where the treatment regimen includes Seroquel XR.

Information on participating psychiatrists will include:

- location of practice (i.e., country, region, and city or town)
- age
- gender
- years in practice
- practice setting (i.e., mental health clinic, university-affiliated hospital, community hospital, private practice office, other)
- proportion of patient volume in hospital versus non-hospital

- approximate proportion of patients with a diagnosis of MDD in their practice

Information on patients will include:

- demographics (date of birth, gender, race)
- source and reason for referral of the patient
- general medical and psychiatric history (i.e., date of first depressive episode, start date of most recent depressive episode, month and year of diagnosis of MDD, total number of depressive episodes over lifetime, number of depressive episodes during the 12 months up to the latest consultation, presence of psychotic symptoms in the past, psychiatric co-morbidities (anxiety disorders, substance use, other Axis I, or other Axis II disorder), other medical co-morbidities (i.e., hypertension, obesity, diabetes, other cardiovascular), ever been hospitalised for a psychiatric condition, ever hospitalised for MDD, and whether hospitalised during most recent depressive episode)

Information on drug utilisation will include, where recorded:

- treatment history including details on current and past drug treatments for MDD (including Seroquel XR) within the past 12 months (historical information based on patient reported drug use may be required if physician has been treating the patient for < 12 months), dose/duration of drugs used to treat MDD (including any drug treatments for MDD noted in the patient's medical record that were prescribed by other physicians), including changes in medication, date of initiation/end for each drug; and whether drug treatments for MDD prescribed with Seroquel XR were still prescribed on the index date; for Seroquel XR treatment details include frequency of prescriptions by dose, prescribed days supply by dose, initial dose, usual (modal) dose, maximum dose
- diagnosis for which Seroquel XR is being prescribed

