9.2 Patient's demographic data and psychiatric history

Summary statistics will be provided by country and overall for patient's demographics data including age, gender, and race, and for patient's medical history including years since first depressive episode, year of MDD diagnosis, number of depressed episodes over lifetime, number of depressive episodes during the 12 months up to the latest consultation, presence of psychotic symptoms in the past, presence of psychotic symptoms at start of Seroquel XR

treatment, psychiatric co-morbidities (anxiety disorders, substance use, other Axis I, or other Axis II disorder), other medical co-morbidity (hypertension, obesity, diabetes, other cardiovascular disorder), ever been hospitalised for a psychiatric condition), as well as for the number of visits to the psychiatrist during the timeframe that Seroquel XR has been prescribed.

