Other Axis 2	Yes / No / Unknown Please specify 1) _____ 2) _____ 3) _____	Past / Current Past / Current Past / Current	Yes / No / Unknown Yes / No / Unknown Yes / No / Unknown	Yes / No / Unknown Yes / No / Unknown Yes / No / Unknown
Hypertension	Yes / No / Unknown	Past / Current	Yes / No / Unknown	Yes / No / Unknown
Obesity	Yes / No / Unknown	Past / Current	Yes / No / Unknown	Yes / No / Unknown
Dyslipidemia	Yes / No / Unknown	Past / Current	Yes / No / Unknown	Yes / No / Unknown
Other cardiovascular	Yes / No / Unknown Please specify 1) _____ 2) _____ 3) _____	Past / Current Past / Current Past / Current	Yes / No / Unknown Yes / No / Unknown Yes / No / Unknown	Yes / No / Unknown Yes / No / Unknown Yes / No / Unknown
Diabetes	Yes / No / Unknown	Past / Current	Yes / No / Unknown	Yes / No / Unknown

Diagnosis of MDD

What was the date of the **1st depressive episode** experienced by this patient (if known)?

___/_____
mo / year

Unknown

What was the date of **diagnosis of MDD?**

___/_____
mo / year

Unknown

Who initially diagnosed this patient with MDD?

Please select one answer only

The investigator

Another psychiatrist

Primary care physician

Other specialist – please specify _____

Unknown

How many **depressive episodes** has this patient experienced in his / her lifetime?

0

1

2

3 or more

Unknown

How many depressive episodes has this patient suffered in the **12 months up to the latest consultation?**

0

1

2

3 or more

Unknown

When did the last depressive episode (prior to the *INDEX DATE*) start?

___/_____
mo / year

Unknown

Has this patient ever been hospitalised for **any** psychiatric condition(s)?

Yes, please specify _____

No

Unknown

In the table below, please specify if this patient has ever been hospitalised for MDD?

Ever Hospitalised for MDD	Number of hospitalisations for MDD
 Yes  No  Unknown	_____ (no. of times)

What is the date of the most recent hospitalisation for MDD?

__ / ____
 mo / year

Unknown

How long was the patient hospitalised for?

__ days

Unknown

In the table below, please specify if, according to the medical record, whether this patient has experienced psychotic episodes? Has this patient experienced psychotic manifestation in the last depressive episode?

Ever experienced psychotic symptoms during a depressive episode?	Experienced during the last depressive episode?

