(1) Specific drug name (generic or brand names)	(2) Start date (day/mth/year) Check for “on demand” or prn use)	(3) End Date (day/mth/year)	(4) Dose (specify Unit)	(5) Did the dose change at initiation of Seroquel XR?	(6) Most recent dose prior to [INDEX DATE] (if different than at initiation)	(7) Date of most recent dose change (day/mth/year)
	___/___/___  prn	___/___/___  Still prescribed at [INDEX DATE]	_____	 Increase  Decrease  Remained the same  Not applicable	_____  Not applicable	___/___/___  Not applicable
	___/___/___  prn	___/___/___  Still prescribed at [INDEX DATE]	_____	 Increase  Decrease  Remained the same  Not applicable	_____  Not applicable	___/___/___  Not applicable
	___/___/___  prn	___/___/___  Still prescribed at [INDEX DATE]	_____	 Increase  Decrease  Remained the same  Not applicable	_____  Not applicable	___/___/___  Not applicable
	___/___/___  prn	___/___/___  Still prescribed at [INDEX DATE]	_____	 Increase  Decrease  Remained the same  Not applicable	_____  Not applicable	___/___/___  Not applicable

Seroquel XR Treatment

Was the patient experiencing psychotic symptoms at initiation of Seroquel XR?

- Yes
- No
- Unknown

Which disorder was Seroquel XR prescribed for?

Please select all that apply

- MDD
- Schizophrenia
- Bipolar disorder
- Other – please specify _____

How many times has the investigator seen this patient since initiation of Seroquel XR?

__ visits

What is your estimate of patient adherence to the prescribed treatment regimen that included Seroquel XR for depression?

___ % of time adherent to prescribed dose(s) (range: 0 – 100%)

(Investigator assessment)

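### No questionnaire item is limited to the time before the treated episode, so Section 9.2's result for past psychotic symptoms is undeterminable for some patients

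*Protocol*

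**What the plan says.** Section 9.2 lists, for summary by country and overall, "presence of psychotic symptoms in the past, presence of psychotic symptoms at start of Seroquel XR" treatment. Section 4.2.2 names the first of these among the psychiatric history variables ("presence of psychotic symptoms in the past, psychiatric co-morbidities") and lists symptoms at prescription separately. Neither section defines the past variable or says how it is derived.

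The Appendix B patient form has three relevant items, each answered Yes, No or Unknown:

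- *Ever*: "Ever experienced psychotic symptoms during a depressive episode".
- *Last*, in the adjacent column: "Experienced during the last depressive episode". The lead-in to the table puts the same question: "Has this patient experienced psychotic manifestation in the last depressive episode".
- *Start*, in the Seroquel XR Treatment part: "Was the patient experiencing psychotic symptoms at initiation of Seroquel XR".

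Two other items bear on the point. One is the count of depressive episodes that the form "has this patient experienced in his / her lifetime" asks for (0, 1, 2, 3 or more, Unknown). The other is the month and year of onset of the last episode: "When did the last depressive episode (prior to the *INDEX DATE*) start".

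**The concern.** The *ever* item has no cut-off. Abstraction takes place after the index date, so a Yes can reflect an earlier episode, the treated episode, or symptoms that first appeared after Seroquel XR was started. Only the first is clearly history at initiation. The comorbidity table on the same form follows its ever-experienced column with a past/current split. The psychotic-symptoms table has no such split.

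Psychotic features describe who is given an antipsychotic for MDD, and patient characteristics by country are the first study objective in Section 1.1. If current psychosis leaks into the history result, a country that uses the drug more in currently psychotic patients will also seem to have more patients with a psychotic past.

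There is a scope mismatch as well. The *ever* column covers only symptoms within depressive episodes, while the variable in Section 9.2 has no such limit.

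**Working it through.** **Which answer patterns fix past history.** Every possible history (symptoms in an earlier episode; in the treated episode before, at or after Seroquel XR start; in a later episode) was mapped to the answers it would produce. Answers are taken as known and correct, and symptoms at start as occurring within a depressive episode. Two meanings of past are tracked because the protocol does not choose between them.

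A. The last episode is the treated episode:

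| Lifetime episodes | Ever | Last | Start | Symptoms in an earlier episode | Symptoms any time before start |
|---|---|---|---|---|---|
| 1 or more | No | No | No | none | none |
| 1 | Yes | Yes | Yes or No | none | undetermined |
| 2 or more | Yes | No | No | present | present |
| 2 or more | Yes | Yes | Yes or No | **undetermined** | **undetermined** |

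B. A new episode began between Seroquel XR start and the index date:

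| Lifetime episodes | Ever | Last | Start | Symptoms in an earlier episode | Symptoms any time before start |
|---|---|---|---|---|---|
| 2 or more | No | No | No | none | none |
| 2 | Yes | either | either | none | undetermined |
| 3 or more | Yes | either | either | **undetermined** | **undetermined** |

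Case B can arise because the date item for the last episode is tied to the index date, and Seroquel XR may have been started up to 9 months before that date. Comparing the two start dates can reveal case B but does not supply the missing history.

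**Illustrative size.** The protocol gives no prevalence of psychotic symptoms or of recurrent episodes, so these inputs are assumptions: true past history p = 10%; psychotic at start s = 10%, 20% or 30%; p and s independent; no other psychotic symptoms.

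Tabulating past directly from *ever* gives p + (1 − p)s:

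- s = 10%: 0.10 + 0.90 × 0.10 = 19%
- s = 20%: 0.10 + 0.90 × 0.20 = 28%
- s = 30%: 0.10 + 0.90 × 0.30 = 37%

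Two countries with the same 10% history but 10% and 30% psychotic at start would differ by 37 − 19 = 18 points.

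Using the *last* column as well gives bounds. Suppose in addition that all patients have two or more episodes, that last is the treated episode, and that psychosis in that episode coincides with psychosis at start. The certain cases (ever Yes, last No) are then p(1 − s) = 9%, 8% or 7%, and the upper limit stays at 19%, 28% or 37%. The gap between the bounds equals s, so it widens with current psychosis.

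Positive association shrinks the inflation. With complete overlap, *ever* equals the larger of p and s: 10%, 20% or 30%. At p = s = 10% there is then no inflation.

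**The case against.** A reader might infer that the form holds only one history item and that past and current symptoms cannot be separated at all. The documents do not support this. The adjacent column asks about the last episode, symptoms at start have their own item, and the lifetime count is collected. When the last episode is the treated one, ever No, ever Yes with last No, and a lifetime count of 1 all settle the earlier-episode question.

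A reader might also infer that the past proportion can never fall below the at-start proportion. That needs past to be read straight from *ever*, which Section 9.2 does not say. Even then it is not guaranteed, because the initiation item is not limited to depressive episodes and both items allow Unknown.

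Further points for the plan are fair. The derivation may be set in an analysis plan that is not shown. Lifetime history is a possible reading of the undefined variable. The illustration rests on assumed, independent prevalences. The study is descriptive, and the result on current psychosis is collected directly and reported under Sections 9.2 and 9.3.

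These points limit the size of the problem but do not remove it. A derivation rule can sort the patterns that resolve; it cannot supply an answer that was never asked for in those that do not. The lifetime reading would make the first result include most of the second, which fits poorly with listing the two side by side.

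**Conclusion.** The point stands in a limited form. As collected, past psychotic history cannot be determined for patients with two or more lifetime episodes who answer Yes to both *ever* and *last*. Where a new episode followed Seroquel XR start, it cannot be determined for any *ever* Yes with three or more episodes. If past means any time before start, it is also undetermined for single-episode patients who answer Yes to both, and for every *ever* Yes in which a new episode followed.

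The number of such patients cannot be derived from the protocol. The 19% to 37% against a true 10% illustrates direct tabulation under stated assumptions and is not an estimate for this study. One descriptive history result and its comparison across countries are affected; no other planned result depends on it. It should still be corrected, because the gap lies in data collection and repairing it later means reopening charts.

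**What to change.** Before abstraction begins:

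1. In the psychotic-symptoms table, add a column (or reword the first) to read: *Psychotic symptoms before the depressive episode for which Seroquel XR was started? Yes / No / Unknown*, not limited to depressive episodes.
2. Tie the last-episode column to the episode in which Seroquel XR was started.
3. Keep the separate item on symptoms at initiation.
4. State in Section 9.2 that the past result uses the new item.

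Symptoms that arose and resolved within the treated episode before initiation would fall outside both Section 9.2 results. The re-anchored column still records that the episode had psychotic features, though without dating them against Seroquel XR start.

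The cost is one eCRF item added or reworded, one re-anchored and one sentence of protocol text. Sections 4.1.2 and 4.2.2 already allow the questionnaire to be revised after pilot testing and advisory board input, and Section 4.1.3 places translation after validation. The downside is some more Unknown answers where charts do not date symptoms.
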